4.3 Study Design

[figure not shown]
The design of this study is a single-arm, phase Ib/II study. The overview of the study is shown in **Figure 1**. A total of 25 patients will be enrolled in the study. Once the recommended phase II dose of grapiprant in combination with eribulin is determined, the remaining patients will be treated in the phase II portion, which adds 14 ± 2 days window period of grapiprant treatment alone before the main study to evaluate the effect of grapiprant treatment in the tumor microenvironment and urine prostaglandin E2 metabolite. We will perform a correlative study by collecting tumor and urine samples at pre-and post-window periods. We will ensure the safety of grapiprant and eribulin combination by phase Ib part and determine efficacy in the phase II part—the detail of the trial design described in the **statistical analysis plan (7.0)**.

The starting dose of grapiprant will be 300 mg BID daily orally. Eribulin will be intravenously administered on day 1 and day 8 of every cycle (starting at the FDA-approved dose of 1.4 mg/m²). We define one cycle as 21 days. We will continue the treatment until disease progression, discontinuation by severe toxicity, death, and patient withdrawal. If the patients cannot continue the eribulin because of its toxicity, they will stop eribulin but continue grapiprant as a single treatment until progression or discontinuation. If the patients cannot continue the grapiprant because of its toxicity, they will be off treatment. We will follow-up with the patients up to 5 years after off-treament (see section 4.9). The follow-up can be performed in the clinic in MD Anderson Cancer Center. If the patient is unwilling to come to the clinic, the follow-up would be done by phone.

We will perform imaging analysis by PET-computed tomography (CT) or CT/bone scan at baseline, after the 2 cycles of proposed treatment (does not includes window period), then at the end of every 3 cycles. The Quantitative Imaging Analyzing Core (QIAC) in MD Anderson Cancer Center will independently evaluate the treatment response based on the imaging results.

Protocol 2021-0077 PI: [name] **Proprietary Information of MD Anderson**

Co-PI: [name] Date: 11/22/2022

Product: Grapiprant

Protocol 2021-0077 Proprietary Information of MD Anderson

PI: [name] Co-PI: [name] Date: 11/22/2022

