4.5 Concomitant Medications/Vaccinations (allowed & prohibited)

Medications or vaccinations prohibited explicitly in the exclusion criteria are not allowed during the ongoing trial. If there is a clinical indication for one of these or other medications or vaccinations prohibited explicitly during the trial, discontinuation from trial therapy or vaccination may be required. The final decision on any supportive therapy or vaccination rests with the investigator and/or the subject's primary physician and will be documented in the subject's chart..

Acceptable Concomitant Medications

All treatments that the investigator considers necessary for a subject's welfare may be administered at the investigator's discretion in keeping with the community standards of medical care. Concomitant medication will be recorded as the standard of care in the subject's medical record.

Prohibited Concomitant Medications

Subjects are prohibited from receiving the following therapies during the study.

- NSAIDs, COX-2 inhibitors.
- Any anti-cancer agents.
- Radiation therapy.
 - Note: Radiation therapy to the symptomatic solitary lesion will be allowed. The treatment will be continued during the treatment.
- Live vaccines within 30 days before the first dose of trial treatment and while participating in the trial. Examples of live vaccines include, but are not limited to, the following: measles, mumps, rubella, chickenpox, yellow fever, rabies, BCG, and typhoid (oral) vaccine. Seasonal influenza vaccines for injection are generally killed virus vaccines and are allowed; however, intranasal influenza vaccines (e.g., Flu-Mist®) are live attenuated vaccines and are not allowed. Any mRNA vaccines for COVID-19 approved under an Emergency Use Authorization will be allowed in any case.
- Subjects who, in the assessment by the investigator, require the use of any of the treatments mentioned above for clinical management should be removed from the trial. Subjects may receive other medications that the investigator deems to be medically necessary. There are no prohibited therapies during the post-treatment follow-up phase.

Investigators should refer to the PI and associated addenda for complete details on the drug interaction potential of grapiprant. Highlights of drug interaction are summarized below.

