4.7 Subject Withdrawal/Discontinuation Criteria

In this study, grapiprant administration will continue until one of the following conditions is observed.

Protocol 2021-0077 Proprietary Information of MD Anderson PI: [name]

Co-PI: [name] Date: 11/22/2022

Disease progression [RECIST Criteria]

Disease progression is defined as the rapid growth of multiple measurable, non-measurable, or new lesions, or at least a 20% increase in the sum of diameters of target (measurable) lesions, taking as reference the smallest sum on study (this includes the baseline sum if that is the smallest on the study). In addition to the relative increase of 20%, the sum must also demonstrate an absolute increase of at least 5 mm. (Note: the appearance of one or more new lesions is also considered progression).

Noncompliance:

If the patient cannot be compliant with the treatment schedule in the absence of toxicity, the study treatment should be discontinued.

Sustained side effects:

Study treatment will be discontinued for patients who have sustained toxic effects attributed to the study drug and require a dose interruption lasting more than 12 weeks.

Initiation of new anticancer treatment:

In patients for whom the investigator determines new treatment for breast cancer is warranted in their judgment, the study treatment may be discontinued.

Patient withdraws consent:

If a patient withdraws consent, the reason(s) for withdrawal must be documented. Patients must be informed that their participation in the study is voluntary and that they may choose not to take part in the study or to stop taking part at any time. If a patient chooses not to take part in the study or discontinue at any time, his/her future medical care or medical benefits will not be affected.

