4.9.1. Definition of Treatment Response

We will perform imaging analysis by CT scan, bone scan, or PET-CT. If the patient had a locoregional disease, a mammogram and ultrasound would be considered. We will evaluate the treatment response in metastasis sites (and primary site, if it exists) and at the following time points: 1) baseline 2) after 2 cycles of proposed treatment (does not include window period) 3) every 3 cycles of proposed treatment. All imaging analysis will be performed based on RECIST criteria. The efficacy outcomes will be CBR, ORR, Time to progression (TTP), Progression-free survival (PFS), and overall survival (OS).

4.9.2. Response will not be considered evaluable in the following categories:

Patients have to receive at least 2 cycles of the combination of eribulin and grapiprant to be evaluated the response. The patients in the following categories are considered to be unevaluable for the response. Those patients who are not evaluable will be excluded from the response's statistical analysis and not be replaced.

Early Deaths:

Patients who die within the first 2 weeks of the initiation of proposed treatment. These cases will be considered treatment failures.

Lost to Follow-up:

Patients for whom there is inadequate information to judge tumor response because of loss of contact with our institution (> 2 months after a missed appointment) and referring physician despite repeated attempts to locate them. These cases will be considered treatment failures in the intent-to-treat analysis.

Major Protocol Violation:

Patients who significantly deviate from the treatment program by either adding or deleting another agent or another therapeutic maneuver or modifying the schedule substantially (delay treatment ≥ 7 days without administration reason) of the drug under evaluation. Patients who do not fulfill the requirements outlined under patient eligibility are also included in this category.

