Research tumor tissue Collection (metastatic site or primary site [if available]) ^e	х			х								
Research Blood/Urine Collection f	Х			Х								
Survival Status h												Х

Product: Grapiprant Protocol 2021-0077 PI: [name] Co-PI: [name] Date: 11/22/2022

- a. Labs, PS and AEs will not be repeated if it was done within 8 (+/-3 days) days before starting treatment on C1D1. PE per physician discretion as clinically indicated at C1D1 and day 1 of all subsequent cycles.
- b. C-reactive protein (CRP) will be obtained at baseline and after the window period of proposed treatment.
- c. As an evaluation of response, imaging analysis will be performed at baseline, after 2 cycles (C3) of proposed treatment, then at the end of every 3 cycles (C6, C9,C12 etc). The other radiological evaluation may include ultrasound, bone scan, and X-rays, brain MRI. PET/CT, chest wall/breast photos as clinically indicated for a standard of care
- d. ECHO, MUGA and EKG will be performed at baseline and as clinically indicated thereafter.
- e. Tumor tissue at the metastatic site or primary site (if available, exclude axillar lymph node) will be collected at baseline and after the window peroid (prior to C1D1 treatment). If the patient had both primary and distant metastasis sites, we would collect sample from the primary site only (excluding axillar lymph node). The biopsy will be done by core needle biopsy, but punch biopsy will be considered if the primary site was a superficial disease. CT-guided biopsy or ultrasonography-guided biopsy will be used based on the location of the metastasis site.
- f. Peripheral blood and urine for correlative studies. Approximately 20 ml of blood (one 10 ml EDTA tube and one 10 ml Red top tube for the serum and PBMCs collection) will be drawn at baseline and after window peroid (prior to C1D1 treatment). For the urine sample, we will collect 10 ml of sample in the urinalysis tube. Urine creatinine will be performed centrally at LabCorp from the frozen urine samples which will be shipped to them in batches.
- g. The mandatory Safety Follow-Up should be conducted approximately 30 days after the last dose of the proposed treatment or before initiating a new anti-cancer treatment, whichever comes first. All AEs that occur before the safety follow-up visit should be recorded. Safety follow-up can be done in the clinic or by phone if the patient is unable to come to the clinic for follow up.

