9.0 DATA MANAGEMENT

9.1 **Data collection plan**

Data collected from the study will be entered in RedCap/Prometheus. The Principal Investigator is responsible for assuring that the data entered into the database are complete and accurate and that data entry is performed promptly.

Data collection for this study including:

- i. demographic information (sex, race, and date of birth).
- ii. physical information (weight and height)
- iii. date of initial breast cancer diagnosis, pathology report of primary breast cancer, biomarker status, and date and location of distant metastases.
- iv. date of disease progression, death.
- v. history of breast cancer surgery and radiation therapy, if applicable.
- vi. date and type of endocrine therapy, chemotherapy, and immunotherapy for metastatic disease.
- vii. all AEs will be collected; however, only ≥ 2 non-hematologic AEs and ≥ 3 hematological AEs will be recorded. Other abnormal laboratory values will not be reported as AEs; however, any clinical consequences of abnormality should be reported as AEs.

Protocol 2021-0077 Proprietary Information of MD Anderson PI: [name]

Co-PI: [name] Date: 11/22/2022

viii. Concomitant medication will be recorded per standard of care in the clinic database and not recorded in the study database.

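### Section 4.5 permits on-study radiotherapy, but no rule says how an irradiated target lesion is scored, so local control by radiation can be counted as clinical benefit

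*Combined protocol and SAP*

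**What the plan says.** Section 4.5 lists radiotherapy among the prohibited therapies and then adds a note: "Radiation therapy to the symptomatic solitary lesion will be allowed. The treatment will be continued during the treatment". These patients therefore stay on study treatment and go on being assessed.

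Section 4.7 holds the plan's only definition of progression: "at least a 20% increase in the sum of diameters of target (measurable) lesions, taking as reference the smallest sum on study", and "the sum must also demonstrate an absolute increase of at least 5 mm". New lesions, and rapid growth of several lesions, also count. Nothing is said about a lesion irradiated on study.

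Section 4.9.1 adds only that "All imaging analysis will be performed based on RECIST criteria". Under section 4.3 the institution's imaging core "will independently evaluate the treatment response based on the imaging results". In the phase II calendar (section 4.13, footnote c), "imaging analysis will be performed at baseline, after 2 cycles (C3) of proposed treatment, then at the end of every 3 cycles".

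Section 4.1 defines CBR as CR, PR, or SD lasting more than 24 weeks. Section 7.0 (300 mg path) continues on at least 2 benefits in 12 patients and declares the treatment promising on at least 5 in 25.

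Among the data items in section 9.1 are "history of breast cancer surgery and radiation therapy, if applicable" and the statement "Concomitant medication will be recorded per standard of care in the clinic database and not recorded in the study database". No item for radiotherapy given during the study is listed.

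**The concern.** A single-arm trial credits every scored benefit to the study treatment. If a measurable target lesion is irradiated and stays in the sum, its shrinkage offsets growth of another target, and a patient whose disease is growing can be carried past 24 weeks as SD. If the irradiated lesion is the patient's only one, radiation control of that lesion alone is enough to count as benefit. Either way a local treatment is scored as drug effect in the primary endpoint, and the decision turns on small counts. Without a written rule, the choice would be made patient by patient in an open-label study.

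**Working it through.** **1. Scan times.** One cycle is 21 days. Scans after 2 cycles and then every 3 cycles fall at weeks 6, 15, 24 and 33 from cycle 1, reading C3, C6, C9 and C12 as the cycle about to start.

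**2. Masked growth.** Illustrative sizes (an assumption): targets A and B are 30 mm each at baseline, and A is irradiated between weeks 6 and 15.

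| Week | A (mm) | B (mm) | Sum, change from smallest sum | Sum if A stayed at 30 | B alone, change from 30 mm |
|---|---|---|---|---|---|
| 6 | 30 | 30 | 60 | 60 | 30 |
| 15 | 20 | 38 | 58 (new smallest) | 68, +13.3% | +26.7%, +8 mm |
| 24 | 15 | 46 | 61, +5.2% | 76, +26.7%, +16 mm: PD | +53.3% |
| 33 | 15 | 52 | 67, +15.5% | 82 | +73.3% |

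Under section 4.7 as written the patient is not PD at week 33 and is scored SD beyond 24 weeks. Only one lesion grows and there is no new lesion, so the several-lesions and new-lesion clauses do not apply. Judged on B alone, PD is reached at week 15.

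**3. General form.** Let f be the irradiated lesion's share of the sum, r its fractional shrinkage, and g the growth of the other targets at which PD is called. With shrinkage and growth in the same scan interval, g = (0.20 + f·r)/(1 − f). For f = 0.5:
- r = 0: 0.20/0.5 = 40%
- r = 0.25: 0.325/0.5 = 65%
- r = 0.5: 0.45/0.5 = 90%

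With the irradiated lesion removed from both sums, the threshold is 20%.

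**4. Other direction.** Assume two 40 mm targets. The irradiated one falls to 20 (smallest sum 60) and then regrows or swells to 32, while the other stays at 40. The sum is 72, +20% and +12 mm, so PD, although the untreated lesion has not changed.

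**5. The plan's own figures.** P(promising) = Σ over x ≥ 2 of Bin(x; 12, p) × P[Bin(13, p) ≥ 5 − x]. This gives 8.33% at p = 0.10 and 86.35% at p = 0.30, matching Table 7 (8.3%, 86.4%). The 10% stated in the text is a ceiling.

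**6. Effect on type I error.** Let c be the chance that radiotherapy turns a non-benefit into a scored benefit, with everyone else at CBR 10%. The documents give no value for c or for the number irradiated. If one patient is certain to be scored as benefit, the claim probability is 20.35% (stage 1 patient) or 16.53% (stage 2 patient). For one irradiated patient the type I error is therefore:
- stage 1: 0.0833 + c(0.2035 − 0.0833). c = 10% gives 9.5%, c = 25% gives 11.3%, and it reaches 10% at c ≈ 14%.
- stage 2: 0.0833 + c(0.1653 − 0.0833). c = 10% gives 9.2%, c = 25% gives 10.4%, and it reaches 10% at c ≈ 20%.

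For two irradiated patients it is (1 − c)²·F0 + 2c(1 − c)·F1 + c²·F2, with F0 = 0.0833:

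| Location | F1 | F2 | c = 10% | c = 25% |
|---|---|---|---|---|
| Both stage 1 | 0.2035 | 0.4080 | 10.8% | 14.9% |
| One in each | 0.1844 (mean of the two) | 0.3733 | 10.4% | 13.9% |
| Both stage 2 | 0.1653 | 0.2688 | 10.0% | 12.6% |

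**7. Effect on power.** One true benefit scored as non-benefit, at CBR 30%, lowers power from 86.35% to 82.8% (stage 1) or 84.9% (stage 2).

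**The case against.** *The lesion stays in the sum only by inference.* Section 4.7 does not say that an irradiated lesion is kept. Section 4.9.1 defers to RECIST, and an independent core reads the scans. Its procedures may deal with this, which cannot be checked from the documents. That stands: the defect is a missing exception, not an instruction to score wrongly. The written rule, followed literally, still gives the result in step 2.

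*Other clauses may apply.* Section 4.9.2 makes a patient unevaluable after a significant deviation such as an added therapeutic maneuver, and section 4.7 lets the investigator stop treatment when new cancer therapy is warranted. Neither clearly covers radiotherapy that section 4.5 permits.

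*The reach is narrow.* This stands. Section 4.2.1 classes bone lesions and inflammatory breast disease as non-measurable, so irradiating them cannot change the target sum. Phase Ib patients need no measurable disease. The 6 + 13 = 19 patients enrolled in phase II on the 300 mg path must have a target lesion, but that does not count patients whose target is irradiated.

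*The data exist.* Radiotherapy is not a medication, section 4.5 requires supportive-therapy decisions to be charted, and this is a single-centre trial. Date and site should be retrievable. What is missing is a listed study item and a route to the imaging core.

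*A reader might infer equal bias in both directions.* Suppose A has shrunk from 30 to 15 mm and stays there while B grows from 30 to 40. The sum goes from 45 to 55 (+22.2%, PD), whereas with A unchanged it would be 70 against 60 (+16.7%, SD). But untreated B has grown 33.3% and 10 mm, so PD is defensible. A clear false progression needs the irradiated lesion itself to swell or regrow, as in step 4.

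**Conclusion.** The point holds as a minor correction. The plan permits radiotherapy to a lesion that may be a target and has no clear rule for scoring it afterwards, and the main risk is false benefit in CBR. For one irradiated patient, type I error stays within the stated 10% unless c exceeds about 14% (stage 1) or 20% (stage 2). For two, the limit is about 7% to 10%, depending on stage. These figures assume the 300 mg path, a number irradiated and a value of c that the documents do not give. A false benefit also needs several things together: a measurable irradiated target that shrinks, another target growing within a window, and no new lesion or non-target progression past 24 weeks; or an only lesion held by radiation.

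A reader might infer that the stated operating characteristics are wrong, or that type I error doubles. Neither is supported. The stated figures reproduce, and the 16.5–20.4% values apply only if one patient is certain to be scored as benefit.

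**What to change.** In section 4.9.1 state that, from the radiotherapy date:
- an irradiated lesion cannot by itself support CR, PR or SD;
- later response and progression are judged on the non-irradiated lesions, with the irradiated target removed from both the current and the reference sums;
- new lesions and non-target progression count as now;
- a patient with no other assessable disease who has not already met CBR counts as non-benefit.

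In section 9.1 add the date and site of on-study radiotherapy as a data item and pass it to the imaging core. In section 7.0 add a sensitivity CBR that counts all irradiated patients as non-benefit.

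Removal is preferable to carrying the lesion at its pre-radiotherapy size. Carrying it forward would still let the other targets grow 40% before PD when f = 0.5, and would count radiation control as stability.

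The cost is a few sentences, one data item and one table. Sample size and cut-offs are unchanged. The downside is that later drug effect on the irradiated lesion is not credited; each true benefit lost this way carries the power cost in step 7.

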4.6 Rescue Medications & Supportive Care

There are no known rescue medications for the study treatments. Subjects should receive appropriate supportive care measures as deemed necessary by the treating investigator. Suggested supportive care measures for the management of adverse events are outlined below. For each disorder, attempts should be made to rule out other causes such as metastatic disease or bacterial or viral infection, which might require additional supportive care. The treatment guidelines are intended to be applied when the investigator determines the events to be related to grapiprant or eribulin. It may be necessary to perform conditional procedures such as bronchoscopy, endoscopy, or skin photography to evaluate the event.

4.7 Subject Withdrawal/Discontinuation Criteria

In this study, grapiprant administration will continue until one of the following conditions is observed.

Protocol 2021-0077 Proprietary Information of MD Anderson PI: [name]

Co-PI: [name] Date: 11/22/2022

Disease progression [RECIST Criteria]

Disease progression is defined as the rapid growth of multiple measurable, non-measurable, or new lesions, or at least a 20% increase in the sum of diameters of target (measurable) lesions, taking as reference the smallest sum on study (this includes the baseline sum if that is the smallest on the study). In addition to the relative increase of 20%, the sum must also demonstrate an absolute increase of at least 5 mm. (Note: the appearance of one or more new lesions is also considered progression).

Noncompliance:

If the patient cannot be compliant with the treatment schedule in the absence of toxicity, the study treatment should be discontinued.

Sustained side effects:

Study treatment will be discontinued for patients who have sustained toxic effects attributed to the study drug and require a dose interruption lasting more than 12 weeks.

Initiation of new anticancer treatment:

In patients for whom the investigator determines new treatment for breast cancer is warranted in their judgment, the study treatment may be discontinued.

Patient withdraws consent:

If a patient withdraws consent, the reason(s) for withdrawal must be documented. Patients must be informed that their participation in the study is voluntary and that they may choose not to take part in the study or to stop taking part at any time. If a patient chooses not to take part in the study or discontinue at any time, his/her future medical care or medical benefits will not be affected.

